This current study (JZP258-401) is a multi-center, open-label, single-arm, phase 4 trial that seeks to build upon the demonstrated benefits of XYWAV and provide further descriptive evidence of safety, effectiveness, tolerability and treatment optimization in participants switching from Xyrem to XYWAV. The study will include comparative assessments related to treatment-based and exposure-related adverse events (AE), tolerability, and therapeutic effectiveness of disease control between Xyrem and XYWAV. Participants will be switched from Xyrem to XYWAV at the same dose and regimen as Xyrem. Once the investigator determines that a stable dose and regimen of XYWAV is achieved, participants will be allowed to dose with or without food. If needed, XYWAV will be titrated to an optimized dose and regimen based on efficacy and tolerability, under the advisement and instruction from the investigator.

Success in this study will be indicated by seamless switching of the majority of participants from Xyrem to XYWAV, with little or no changes in dose strength or regimen. Additionally, evidence will be provided to support participant preference for XYWAV based on its lower level of sodium, potentially improved tolerability profile, a safety profile typical of oxybate, and similar disease control as participant's current Xyrem dose and regimen. Collectively, these data are expected to expand the knowledgebase of clinical experience in the population of participants with narcolepsy transitioning from Xyrem to XYWAV.

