6. ANALYSIS SETS

For purposes of analysis, the following populations are defined:

Table 1Analysis Set

Analysis Set	Description
All Screened	The All Screened Analysis Set will include all subjects who provided a signed informed consent for this study.
	This analysis set will be used to summarize the number of screened, screen failure and enrolled subjects.
Enrolled	All participants who sign the informed consent form and meeting all eligibility criteria for the study.
	This analysis set will be used to summarize participant disposition, major protocol deviations (as classified in CTMS), and inclusion/exclusion from the Safety Analysis Set, including reasons for exclusion from it.
Safety	The Safety Analysis Set will include all participants in the Enrolled Analysis set who take at least one dose of Xyrem after providing informed consent.
	This analysis set will be used for summaries of all endpoints, except those which only pertain to data captured during the Intervention Period.

Analysis Set	Description
XYWAV Safety	The XYWAV Safety Analysis Set will include all participants in the Safety Analysis Set who take at least one dose of XYWAV.
	This analysis set will be used for summaries of all endpoints which pertain to only data captured during the Intervention Period.
XYWAV Efficacy	The XYWAV Efficacy Analysis Set will include all participants in the XYWAV Safety Analysis Set who finish the course of study.
	This analysis set will be used for summaries of all endpoints which pertain to only data captured during the Intervention Period.

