7.1. General Methods

Assessments of all study endpoints (as listed in Section 4.2 will be summarized descriptively. Formal hypothesis testing will not be performed.

In general, categorical variables will be reported as frequency and percent. Continuous variables will be reported as the number of participants, mean, standard deviation (SD), or standard error (SE), median, minimum and maximum or range.

For quantitative measures, change from baseline will be calculated as: Change from baseline = test value at Visit X – test value at baseline

All data will be summarized in tables with a single "overall" column for statistics. As applicable, data will be summarized by visit and/or study period.

All summaries, statistical analyses, and individual participant data listings described below will be completed using Version 9.4 or later of the SAS Statistical Analysis System (SAS Institute, Inc. Cary, NC).

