10.2. Adverse Events

Adverse events (AEs) occurring from the initial participant ICF signature date until the end of Safety Follow-up visit will be reported. If the Investigator becomes aware of a serious adverse event (SAE) within 30 days after the last dose of study drug XYWAV, the event must also be reported. In addition, any SAE assessed as related to study drug or procedure by the Investigator must be reported regardless of time elapsed after study termination.

Adverse events recorded in the case report form will be coded to system organ class (SOC) and preferred term using the Medical Dictionary for Regulatory Activities (MedDRA), Version 24.0. The investigator will assess the relationship of each AE to study drug. AE with a missing relationship to study drug will be reported as related in the summaries. Severity, as determined by the Investigator using National Cancer Institute (NCI) common terminology criteria for adverse events (CTCAE) version 5.0 or higher, will be classed as mild, moderate, severe, life-threatening or fatal. An AE with missing severity will be reported as missing in the summaries.

Note that participants who acquire COVID-19 or report AEs due to the COVID-19 public health emergency (eg anxiety) while on study will be coded accordingly and included in the adverse event summaries.

AEs are defined in this study as follows (Protocol Appendix 7):

- A 'Xyrem-emergent AE' refers to an AE that began or worsened in the period following signing of the informed consent and before administration of the first study intervention (XYWAV) dose (i.e., including the Screening period through the Baseline [Xyrem-stable dose and regimen] period till the first dose of XYWAV)
- A treatment-emergent adverse event (TEAE) refers to an AE that either began or worsened after administration of the first dose of study intervention drug (XYWAV) to End of Treatment (ET) period (prior to the Safety Follow-up period).
- Safety follow-up AEs are defined as occurring after the last dose date until 30 days after the last dose date
- Unless specified, the term AEs will include both Xyrem-emergent AEs, TEAEs and Safety follow-up AEs.
- Safety follow-up AEs will not be considered as either Xyrem-emergent AEs or TEAE. They will not be included into summary tables but will be presented in listings.
- Xyrem-emergent AE related summaries will be based on safety analysis set.
- TEAE related summaries will be based on XYWAV Safety analysis set.

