An overall summary on Xyrem-emergent AE and TEAE with following categories will be provided:

- Subjects with any Xyrem-emergent AE/TEAE
- Subjects with any drug-related Xyrem-emergent AE/TEAE
- Subjects with any serious Xyrem-emergent AE/TEAE
- Subjects with any Xyrem-emergent AE/TEAE by severity
- Subjects with any Xyrem-emergent AE/TEAE with outcome as death
- Subjects with any Xyrem-emergent AE/TEAE leading to drug withdrawal
- Subjects with any Xyrem-emergent AE/TEAE leading to drug dose reduction
- Subjects with any Xyrem-emergent AE/TEAE leading to drug dose increase
- Subjects with any Xyrem-emergent AE/TEAE leading to drug interruption

In addition, subject incidence of Xyrem-emergent AEs/TEAEs will be summarized by following:

- SOC and PT
- PT only
- Maximum Severity by SOC and PT
- Drug-related by SOC and PT
- Xyrem-emergent AE/TEAE leading to drug withdrawal by SOC and PT

For data listings, all following will be presented:

- All AEs
- AEs with an outcome of death
- AEs leading to drug withdrawal
- Serious AEs

If a participant has multiple events with the same PT occurring in different periods, the event will be reported for each of those periods. Participant incidence of AEs by SOC and PT tables are sorted by SOCs (alphabetical order) and then by PTs (descending order) within each SOC for the overall frequency. For summaries by PT only, PTs will be sorted in descending order of overall frequency.

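### No planned AE summary shows Xyrem-emergent AEs in the participants who switched, so the Xyrem versus XYWAV AE comparison rests on two nested but unequal analysis sets

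*SAP*

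**What the plan says.** SAP 10.2 assigns a different analysis set to each type of AE: "Xyrem-emergent AE related summaries will be based on safety analysis set" and "TEAE related summaries will be based on XYWAV Safety analysis set".

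SAP section 6 defines the sets in sequence:

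- Enrolled set: "All participants who sign the informed consent form and meeting all eligibility criteria for the study". Screen failures are therefore outside every set below.
- Safety set: "The Safety Analysis Set will include all participants in the Enrolled Analysis set who take at least one dose of Xyrem after providing informed consent".
- XYWAV Safety set: "The XYWAV Safety Analysis Set will include all participants in the Safety Analysis Set who take at least one dose of XYWAV".

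SAP 10.2 then brings the two AE types together: "An overall summary on Xyrem-emergent AE and TEAE with following categories will be provided". Tables by SOC and PT, by maximum severity, by relationship and for drug withdrawal follow for both types. No column layout is given. SAP 7.1 says only that tables have one overall column and that "As applicable, data will be summarized by visit and/or study period".

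The intention to compare is in Protocol section 2: "The study will include comparative assessments related to treatment-based and exposure-related adverse events (AE), tolerability", with therapeutic effectiveness also named, between Xyrem and XYWAV.

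**The concern.** Each participant's own Xyrem period is the only comparator in this single-arm design. Its strength is that the same people are observed on both drugs. The AE summaries lose part of that strength, because a participant who leaves before the first XYWAV dose stays in the Xyrem numerator and denominator and is in neither for XYWAV.

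The SAP expects such exits. Section 7.2.3 has a mapping rule for discontinuation during the Baseline Period, and section 7.2.4 says that dropouts are not replaced. The AE summaries also differ here from the effectiveness summaries, which SAP 9.1 bases on the XYWAV Safety and XYWAV Efficacy sets, so that baseline and follow-up there describe people who switched.

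At stake is how a difference between the two AE percentages is read. Part of it could reflect who is counted and not which drug was taken. The figures may be shown externally at the optional interim analyses (SAP 5.5), and the study data may be used in label discussions (SAP 5.1).

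**Working it through.** **No figure to reproduce.** The documents give no AE rate, no pre-switch dropout rate and no sample-size calculation. The planned total of 100 (SAP 5.3) is declared as sufficient. The size below therefore rests on stated assumptions.

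**Which participants differ.** The XYWAV Safety set is contained in the Safety set. The difference between them is exactly the d participants who took Xyrem after consent and never took XYWAV.

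**Formula.** Let N be the Safety set, p the Xyrem-emergent AE incidence in switchers and q the incidence in non-switchers.

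- Tabulated Xyrem incidence: [(N − d)p + dq]/N
- Incidence in the people who are also in the TEAE summary: p
- Shift = tabulated − p = (d/N)(q − p)

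**Numbers, assuming N = 100 and p = 20%** (shift in percentage points):

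| d | no leaver has an AE (q = 0) | leavers at the switchers' rate (q = 20%) | twice the rate (q = 40%) | every leaver has an AE (q = 100%) |
|---|---|---|---|---|
| 0 | 0 | 0 | 0 | 0 |
| 2 | −0.4 | 0 | +0.4 | +1.6 |
| 5 | −1.0 | 0 | +1.0 | +4.0 |
| 10 | −2.0 | 0 | +2.0 | +8.0 |
| 15 | −3.0 | 0 | +3.0 | +12.0 |

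Example: d = 5, q = 100% gives (5/100)(100 − 20) = +4.0.

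**Other values of p, d = 5:** −0.5 to +4.5 for p = 10%; −1.5 to +3.5 for p = 30%; −2.5 to +2.5 for p = 50%.

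**Small denominators.** At an interim analysis of about 25 participants, suppose 5 have a Xyrem-emergent AE and one of those 5 leaves before the switch. The tabulated figure is 5/25 = 20.0%; in switchers it is 4/24 = 16.7%. The NT1 and NT2 summaries (SAP 9.1.7) also have smaller denominators.

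**Would the protocol's single Safety set (Protocol 9.3) solve it?** No. It would put people never exposed to XYWAV in the TEAE denominator. A true 30% TEAE incidence would read 0.30 × 95/100 = 28.5% with 5 non-switchers and 0.30 × 90/100 = 27.0% with 10.

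**Observation windows, a separate matter.** Xyrem-emergent AEs run from consent: up to 30 days of Screening plus 14 of Baseline, so up to 44 days. XYWAV covers 6 × 7 = 42 days. If only Baseline-period AEs are used, as Protocol 9.4.4 also plans, it is 14 days against 42. Under an assumed constant hazard, 10% over 14 days corresponds to 1 − 0.9³ = 27.1% over 42 days. That gap can exceed any shift in the table above.

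**The case against.** Counting each period's AEs among those exposed in that period is usual safety practice, and each incidence is correct for its own set. That stands. The study is descriptive, no between-period AE contrast or test is specified, and SAP 7.6 discloses the added analysis sets. That also stands, and it limits the point to how the comparison is presented.

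Much of the mismatch will be visible. SAP 8.2 tabulates disposition by period with reasons, and SAP 10.2 tabulates and lists Xyrem-emergent AEs leading to drug withdrawal. This answers the point only in part: a leaver whose AE was unrelated to leaving still counts in the Xyrem percentage, and the reader would have to rebuild the switchers' figure from listings.

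A reader might infer three stronger things that the documents do not support.

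- *That the two summaries describe different people.* They do not. The sets are nested, every switcher is in both, and the difference may be nobody.
- *That the mismatch must favour XYWAV.* A leaver without an AE lowers the Xyrem percentage. Protocol 7.1 and 7.2 list exits that need no AE, such as participant request and non-compliance, and 7.1 adds positive alcohol or drug screens, which are scheduled before the switch as well. Participants enter on a tolerated Xyrem dose that has been stable for at least 2 months, so assuming that every leaver had an AE is an extreme case.
- *That a side-by-side table with a between-drug contrast is planned.* SAP 10.2 plans one overall summary of both AE types and does not fix its layout.

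The unequal observation windows do not rebut the point. They are a further limit on the same comparison.

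**Conclusion.** The point holds in a limited form. The announced Xyrem versus XYWAV AE comparison uses two nested sets, and nothing in SAP 10.2 gives the Xyrem incidence in the people who went on to XYWAV. The individual percentages are sound.

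The size cannot be known from the documents. Assuming 100 in the Safety set and 20% incidence in switchers, 5 pre-switch losses move the Xyrem figure by between −1.0 and +4.0 points and 10 losses by between −2.0 and +8.0. If leavers have twice the switchers' rate, the shift is +1.0 and +2.0. It is zero if nobody leaves or if leavers and switchers have the same rate. The direction favours XYWAV only when q exceeds p. Because neither size nor sign can be known in advance, the common-set summary is best specified before results are seen. This is an inexpensive improvement to a descriptive comparison and does not call the safety analysis itself into question.

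**What to change.** Keep both existing summaries and add to SAP 10.2:

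> Wherever Xyrem-emergent AEs and TEAEs are presented together or compared, Xyrem-emergent AEs will also be summarised for the XYWAV Safety Analysis Set, so that both periods describe the same participants; the number of Safety Analysis Set participants who never took XYWAV, and their reasons, will be footnoted.

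The full Safety Analysis Set table must stay. A switchers-only table drops every AE that ended participation before the switch, so it cannot replace the complete record of events on Xyrem.

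The cost is one sentence in the SAP and a repeat of existing AE tables on a set already defined. No new data are needed. The shift (d/N)(q − p) then disappears from the comparison.

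The change does not correct the unequal observation windows. State these next to any comparison: up to 44 days on Xyrem against 42 on XYWAV, or 14 against 42 if only the Baseline period is used.

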9.4.1.2. Definition of Study Periods for Analysis

The Baseline (Xyrem) Period refers to a 2-week duration in which participants remain on a stable Xyrem dose and regimen, with or without concomitant anticonvulsants or stimulants. All data collected prior to the participant's first dose of XYWAV will be included in this period.

The Intervention (Open-label Treatment Conversion and Optimization) period refers to the 6-week duration in which the participant's treatment is transitioned from Xyrem to XYWAV. All data collected after the first dose of XYWAV will be included in this period (which does not include the Safety Follow-up period).

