9.4.4. Safety And Tolerability Analysis

All safety and tolerability analyses will be conducted in the Safety Population, based on key endpoints are summarized below. Additionally collected safety data will be summarized, as appropriate.

Adverse Event Analyses

AEs will be mapped to system organ classes (SOC) and preferred terms (PT) in alignment with Medical Dictionary for Regulatory Activities (MedDRA) criteria. AEs are defined in this study as follows ([Appendix 7](#)).

- A ‘Xyrem-emergent AE’ refers to an AE that began or worsened in the period following signing of the informed consent and before administration of the first study intervention (XYWAV) dose (ie, including the Screening period through the Baseline [Xyrem-stable dose and regimen] period)
- A treatment-emergent adverse event (TEAE) refers to an AE that either began or worsened after administration of the first dose of study intervention drug (XYWAV) to ET (prior to the Safety Follow-up period).
- Unless specified, the term AE will include both Xyrem-emergent AEs and TEAEs
- Any AEs occurring in the post-intervention Safety Follow-up period will not be considered as either Xyrem-emergent AEs or TEAE; these will not be included as part of safety and tolerability analyses, but listed separately.

Xyrem-emergent AEs (overall and during the Baseline period), TEAEs, SAEs, AEs leading to discontinuations and fatal AEs will be summarized. All AEs will be summarized by maximum severity.

The population incidence of Xyrem-emergent AEs, TEAEs, SAEs, AEs leading to discontinuations and any fatal AEs will be presented by MedRA SOC and PT categories. PT summaries may also be provided, as appropriate.

If a participant has multiple events with the same PT occurring in different periods, the event will be reported for each of those periods. Multiple increases in severity will only be counted as one AE.

Nausea Visual Analog Scale (NVAS)

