7.2.2. Study Day

The screening period is from Day -30 to Day -1. The 2-week baseline period is Day 1 to Day 14. Participants on a stable dose and regimen of Xyrem will be switched to XYWAV treatment at the beginning of the Intervention (Open-label Conversion and Treatment Optimization) period, starting the night of Visit 3/Day 15 and continue through to the End of Treatment (ET) (Visit 8) or Early Discontinuation (E/D) visit, as applicable.

Study day will be calculated as:

Study Day = (the date of assessment or event - the first day of the baseline period (Visit 2)) + 1 XYWAV Study Day = (date of assessment - date of first dose of XYWAV) + 1

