7.2.3. Visit Windows

Except where specified, all data will be summarized using the CRF visit at which the data was collected. Where data is captured at an Early Termination visit, those data will be summarized with the regular visit at which the assessment would have been captured, relative to the study period during which the participant withdrew. For example:

- If a participant early discontinues during the Baseline Period, i.e. prior to the first dose of XYWAV, then data should be mapped to Visit 3.
- If a participant early discontinues during the Intervention Period, i.e. after at least one dose of XYWAV, then data should be mapped to the next scheduled visit at which those data would have been captured, based on the Schedule of Assessments.

For data captured independent of a CRF visit, eg, Adverse Events, Concomitant Medications and Cataplexy Diary, the following rules will apply:

- If the reported date is on or prior to first dose of XYWAV then the data will be considered to be included into the Xyrem Baseline Period for summaries
- If the reported date is after the first dose of XYWAV while on or prior to the completion of treatment or early discontinuation, then the data will be considered to be included into the XYWAV Intervention Period for summaries.

Unscheduled visits in general will not be mapped (excluded from analyses) when the corresponding scheduled visit is present. Unscheduled visits will only be mapped when the scheduled visit is missing. If more than 1 unscheduled assessments are available, choose the one with the assessment date closer to the target study day specified below, if 2 assessments are equally close to the target day (but on different sides), the latter assessment will be chosen. In addition, unscheduled visits with the assessment date earlier than the date of first dose of XYWAV, or participants early discontinue the study prior to the first dose of XYWAV, the data can only be mapped up to Visit 3. If the assessment date is later than the date of first dose of XYWAV, the unscheduled data should not be mapped to any visit prior to Visit 3.

Study Period	Study Visit	Target Study Day
Baseline	Visit 2	1
Intervention	Visit 3	15

Intervention	Visit 4	22
Intervention	Visit 5	29
Intervention	Visit 6	36
Intervention	Visit 7	43
Intervention	Visit 8	57

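### Xyrem-emergent AEs and TEAEs are paired as crude incidences over windows of different, participant-specific length, and the Xyrem AE window is defined inconsistently

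*SAP*

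**What the plan says.** Protocol 9.4.4 sets the statistic: "The population incidence of Xyrem-emergent AEs, TEAEs, SAEs, AEs leading to discontinuations and any fatal AEs will be presented". SAP 10.2 follows it, stating that "subject incidence of Xyrem-emergent AEs/TEAEs will be summarized by following" a set of paired lists of Xyrem-emergent AEs and TEAEs, counted as participants with an event. Neither document plans an AE rate or person-time. SAP 10.1.1 summarises days of exposure to each drug, but counts Xyrem only in the baseline period and does not link those days to the AE tables.

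The windows are described in several places:

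- **Protocol 9.4.4 and SAP 10.2:** Xyrem-emergent AEs start at consent. In the SAP's words, the window runs "including the Screening period through the Baseline [Xyrem-stable dose and regimen] period till the first dose of XYWAV".
- **Protocol Appendix 7:** Xyrem-emergent AEs are those associated with Xyrem during the initial Baseline period. Both sections above cite this appendix for their definition.
- **Protocol 9.4.1.2:** Baseline is a 2-week period, but everything collected before the participant's "first dose of XYWAV will be included in this period".
- **SAP 7.2.2:** "The 2-week baseline period is Day 1 to Day 14".
- **SAP 7.2.3:** an AE whose reported date "is on or prior to first dose of XYWAV then the data will be considered to be included into the Xyrem Baseline Period", with no lower limit.
- **Protocol 9.4.4, list of summaries:** "Xyrem-emergent AEs (overall and during the Baseline period), TEAEs, SAEs, AEs leading to discontinuations and fatal AEs will be summarized", which treats the Baseline period as narrower than the whole Xyrem window.

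SAP 10.2 lists no separate Baseline-period table, and SAP 7.6 records no change on this point. The end of the TEAE window is also unclear. SAP 10.2 runs TEAEs to End of Treatment, but classes events after the last dose date as Safety follow-up AEs, which are listed and kept out of the tables.

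**The concern.** The Xyrem period is the only within-study reference for XYWAV safety. Protocol section 2 promises comparative AE assessments, Protocol 4.1 says the data may support label discussions, and Protocol 9.5 allows interim data to be presented externally. Readers will therefore set the paired percentages side by side. The percentage of participants with at least one event grows with the length of observation, so unequal windows can produce a difference when the event rates are the same, or hide one when they differ. Because screening time varies by participant, a reader of the tables cannot allow for this.

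The inconsistent definitions add a second problem. Two programmers working from the same documents could reasonably produce different Xyrem tables, one with screening events and one without.

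**Working it through.** **Inputs.** Screening up to 30 days, Baseline 2 weeks, Intervention 6 weeks, Safety Follow-up 2 weeks, and 14 weeks per participant from consent to completion (Protocol Table 2). About 3 to 3.5 months per participant (Protocol 4.1). Target Day 15 for Visit 3 and Day 57 for Visit 8 (SAP 7.2.3).

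**Reproducing the plan's durations.** 30 + 14 + 42 + 14 = 100 days = 14.3 weeks, against 14 stated. From the SAP target days, 57 - 15 = 42 days on XYWAV and 15 - 1 = 14 days of Baseline.

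**Screening time implied by the stated durations.** The fixed periods take 14 + 42 + 14 = 70 days.

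- 14 weeks: 98 - 70 = 28 days, so the Xyrem window is 14 + 28 = 42 days, equal to the TEAE window.
- 3 months (about 91 days): 91 - 70 = 21 days, so the Xyrem window is 35 days.
- 3.5 months (about 106.5 days) would leave 36 days, beyond the 30-day limit.

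**Crude ratio at equal rates.** Assume the same constant hazard h per week on both drugs and complete follow-up. Then incidence = 1 - exp(-h × d / 7), with d = 42 for XYWAV and d = 14 + s for Xyrem, where s is the number of screening days.

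| s (days) | Xyrem incidence at h = 5% (XYWAV 25.9%) | Ratio at h = 0.5% | Ratio at h = 5% | Ratio at h = 10% |
|---|---|---|---|---|
| 0 (Day 1 to 14 only) | 9.5% | 2.97 | 2.72 | 2.49 |
| 1 | 10.2% | 2.77 | 2.55 | 2.34 |
| 14 | 18.1% | 1.49 | 1.43 | 1.37 |
| 21 | 22.1% | 1.20 | 1.17 | 1.15 |
| 28 | 25.9% | 1.00 | 1.00 | 1.00 |
| 30 | 27.0% | 0.96 | 0.96 | 0.97 |

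Setting the ratio to 2 and solving for s gives 6.8 days at h = 0.5% and 3.9 days at h = 10%. A ratio above 2 therefore needs screening shorter than about 4 to 7 days.

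**Date rule.** SAP 7.2.3 assigns the whole of Day 15 to Xyrem, which makes 15 Baseline days. At h = 5% the ratio becomes 2.40 (s = 1), 1.14 (s = 21) and 0.98 (s = 28).

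**Choice of rate.** Dividing participants with an event by whole-window time over-corrects. At h = 10% and s = 1 it gives 45.1% / 6 weeks = 7.5 against 19.3% / 2.143 weeks = 9.0 per 100 person-weeks, a ratio of 0.83. If time stops at the first event, expected person-time is (1 - exp(-h × d / 7)) / h, so the rate equals h in either window. This follows from the constant-hazard assumption and is not evidence about the trial.

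**What a rate can hide.** A hazard of 15% in week 1 and 3% in each of weeks 2 to 6 gives 25.9% incidence and 0.2592 / 4.925 weeks = 5.26 per 100 person-weeks. That is close to a constant 5%, despite a threefold hazard in week 1.

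**The case against.** The strongest reply is that the study is descriptive. Its objective is to describe, no test is planned, no AE difference or interval is planned, and the comparative language sits in an introductory sentence and not in an endpoint. This limits the consequence to interpretation. It does not remove the point, because SAP 10.2 pairs the two sets of counts and readers will compare them.

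A second reply is that the plan's own durations bring the windows close together: 14 weeks implies equal windows, and 3 months implies a ratio of at most 1.20. This also stands. They are planning estimates, possibly at the upper end, but they are the only duration figures available. A reader might infer from the short-screening rows that XYWAV will look two to three times worse than Xyrem. The documents do not support that, since they give no actual screening lengths and the ratio falls slightly below 1 at 30 days.

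A third reply is that SAP 7.2.3, the rule that names adverse events, puts all pre-XYWAV events into Baseline, so that one Xyrem table meets both protocol requests. On that reading nothing was dropped. A reader might infer that the SAP omitted a required table, but this follows only if Baseline means Day 1 to 14.

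Finally, rates have limits of their own. They assume that an average is informative, they can hide clustering after the switch, and they do not correct for the larger number of AE contacts during XYWAV.

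**Conclusion.** The point holds as a limited one. Crude incidences over windows of unequal, participant-specific length are paired without time at risk, and the Xyrem AE window is defined inconsistently across Protocol 9.4.1.2, 9.4.4 and Appendix 7 and SAP 7.2.2, 7.2.3 and 10.2. Under equal constant hazards and full follow-up, the distortion ranges from nil at the screening length implied by 14 weeks to 15% to 20% at that implied by 3 months. It is larger only with shorter screening or a Day 1 to 14 window. Size and direction in the actual data cannot be known from the documents.

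A reader might also infer that the Xyrem figure is materially lowered because the SAP's Enrolled set, in which the Safety set is nested, is restricted to "All participants who sign the informed consent form and meeting all eligibility criteria for the study". Removing a participant whose screening event caused ineligibility does lower it, but nothing in the documents allows the effect to be sized.

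Severity is minor to moderate: descriptive interpretation is affected, not error rates.

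**What to change.** Keep the crude tables, and:

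1. Reconcile the Xyrem-emergent AE window and the meaning of Baseline across Protocol 9.4.1.2, 9.4.4 and Appendix 7 and SAP 7.2.2, 7.2.3 and 10.2. Within SAP 10.2, reconcile the end of the TEAE window (End of Treatment or last dose date).
2. For any AE, drug-related AE, SAE and common preferred terms, add first-event rates per 100 person-weeks with 95% CI. Time runs from the start of the reconciled window to the first such event or the end of that same window, so that no time is counted in which an event could not be assigned to it. Do not use the SAP 10.1.1 Xyrem exposure as the denominator unless the reconciled window is Baseline only.
3. If Baseline means Day 1 to 14, add the Baseline-period Xyrem AE summary as a rate, or record its omission in SAP 7.6.
4. Report the distribution of window lengths. Footnote that rates do not remove the asymmetry between participants stable on Xyrem and those newly switched, early clustering after the switch, or the unequal number of AE contacts.

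The cost is a few extra tables from dates already collected. The downside is wide intervals. With 100 participants, 5% per week and full follow-up (assumptions), 26 first events in 518 XYWAV person-weeks give a 95% CI of 3.3 to 7.3 per 100 person-weeks. Ten first events in 190 Day 1 to 14 Xyrem person-weeks give 2.5 to 9.7. Three participants with an SAE in 591 person-weeks (each at week 3, so 600 - 9) give 0.51, with a 95% CI of 0.10 to 1.48.
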